8.1 Modified Intent-to-Treat

The modified Intent-to-Treat (mITT) population includes all randomized subjects with one post baseline efficacy assessment. Efficacy analysis will be performed on the mITT population. Subjects in the mITT population will be analyzed as randomized.

8.2 Per Protocol

The PP population includes subjects in the mITT population who do not have significant protocol deviations and who complete the study. Protocol deviations will be assessed and determined prior to database lock and unmasking. Subjects in the PP population will be analyzed as treated.

8.3 Safety

The Safety population includes all subjects who have received at least one dose of the investigational product. The Safety population will be analyzed as treated and will be used for the safety analyses. No data will be excluded for any reason.

Summaries of the comfort data from the Comfort Assessment will be performed on the Safety population from that Assessment. The statistical analysis of safety data will be performed for the Safety population, separately for the Comfort Assessment and the Safety and Efficacy Assessment. The analysis of baseline and all efficacy data in the Safety and Efficacy Assessment will be performed for the mITT population. The efficacy analyses may also be performed on the PP population as sensitivity analyses.

9. General Statistical Considerations

9.1 Unit of Analysis

Safety endpoints will be analyzed for both eyes. For efficacy endpoints, the unit of analysis will be the "worst eye" as defined by the following:

Worst Eye: Eyes are eligible for analysis if they meet all of the inclusion criteria. In the case that both eyes are eligible for analysis, the study eye will be the eye with worse (higher) increase in total corneal staining change from pre-CAE® to post-CAE® at Visit 2b on the Ora Calibra® scale. If the increase in total corneal staining is the same in both eyes, then the study eye will be the eye with the largest increase in ocular discomfort from pre-CAE® to post-CAE® at Visit 2b. If the ocular discomfort symptom increase is the same in both eyes, then the right eye will be selected as the worst eye.

9.2 Missing or Inconclusive Data Handling

The efficacy analyses will be performed using observed data. In addition, for key endpoints of corneal staining and ocular discomfort, missing data will be imputed using the following methods:

- Using the last observation carried forward (LOCF) imputation method for missing values
- Using multiple imputation methods to account for missing data

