## General Statistical Methods and Types of Analyses

### Analysis Populations:

- Modified Intent-to-Treat Population – The modified intent-to-treat (mITT) population includes all randomized subjects with at least one post visit 2 study assessment. Efficacy analysis will be performed on the mITT population. Subjects in the mITT population will be analyzed as randomized.
- Per Protocol Population – The per protocol (PP) population includes subjects in the mITT population who do not have significant protocol deviations and who complete the study. Protocol deviations will be assessed prior to database lock and unmasking. Subjects in the PP population will be analyzed as treated.
- Safety Population – The safety population includes all subjects who have received at least one dose of the investigational product. Subjects in the Safety population will be analyzed as treated.

Summaries of the comfort data from the Comfort Assessment will be performed on the safety population from that Assessment. The statistical analysis of safety data will be performed for the safety population, separately for the Comfort Assessment and the Safety and Efficacy Assessment. The analysis of baseline and all efficacy data in the Safety and Efficacy Assessment will be performed for the mITT population. The efficacy analyses may also be performed on the PP population as sensitivity analyses.

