Subjects who terminate early during the treatment period will be asked to complete safety assessments prior to commencement of any alternative dry eye treatment (if possible) according to PI judgment. Subjects who are terminated early from the study will not be replaced.

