### **Early Termination/Discontinuation**

If a subject is discontinued from the study prior to Visit 8a or 4b, then all safety evaluations that were to be performed at the Visit should be performed on the day of discontinuation (early termination) or at the discretion of the investigator.

Adverse Events (both elicited and observed) and SAEs will be monitored throughout the study. The investigator will promptly review all adverse events (both elicited and observed) for accuracy and completeness. All adverse events will be documented on the appropriate source document and case report form.

If a female reports a pregnancy or has a positive pregnancy test during the study the investigator will notify Ora immediately. The investigator shall request from the subject and/or the subject’s physician copies of all related medical reports during the pregnancy and shall document the outcome of the pregnancy. The investigator will retain these reports together with the subject’s source documents and will provide a copy of all documentation to Ora.

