mmHg	Millimeters of Mercury
OD	Right Eye
OPI	Ocular Protection Index
OS	Left Eye
OSDI [®]	Ocular Surface Disease Index
OU	Both Eyes
OTC	Over-the-counter
PMNs	Polymorphonuclear Leucocytes
PP	Per Protocol
PT	Preferred Term
TID	Three Times a Day
SAE	Serious Adverse Event
SAP	Statistical Analysis Plan
SDC	Statistics and Data Corporation
SOC	System Organ Class
SOP	Standard Operating Procedure
TFBUT/TBUT	Tear Film Break-up Time
TEAE	Treatment Emergent Adverse Event
VA	Visual Acuity
VAS	Visual Analogue Scale
WHO	World Health Organization

1. Introduction

The purpose of this statistical analysis plan (SAP) is to describe the planned analyses and reporting for protocol TOP1630-TV-04, version 2.0 dated 20Jan2017.

This SAP is being written with due consideration of the recommendations outlined in the most recent International Conference on Harmonization (ICH) E9 Guideline entitled Guidance for Industry: Statistical Principles for Clinical Trials and the most recent ICH E3 Guideline, entitled Guidance for Industry: Structure and Content of Clinical Study Reports (CSR).

This SAP describes the data that will be analyzed and the subject characteristics, efficacy, and safety assessments that will be evaluated. This SAP provides details of the specific statistical methods that will be used. The statistical analysis methods presented in this document will supersede the statistical analysis methods described in the clinical protocol. If additional analyses are required to supplement the planned analyses described in this SAP they may be completed and will be identified in the CSR.

2. Study Objectives

The primary objective of this study is to compare the safety and tolerability of TOP1630 Ophthalmic Solution to placebo. The secondary objectives are to compare the efficacy of TOP1630 Ophthalmic Solution to placebo for the treatment of the signs and symptoms of dry eye syndrome.

3. Study Variables

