16.14 Daily Diary

Each day during the at-home dosing period (including the run-in period), subjects will grade the severity of their dry eye symptoms in their diary in the morning, afternoon and evening prior to each dose. Subjects will rate the severity of each of the following symptoms, with regard to how both their eyes feel:

The individual symptoms will be analyzed using a two-sample *t*-test to compare the two treatment groups. This analysis will be completed separately for the morning, afternoon and evening scores as well as the daily average score. Additionally, the average score for each time point (morning, afternoon, evening and daily average) will also be analyzed separately using a Wilcoxon rank sum test and an ANCOVA model adjusting for baseline, where baseline scores are calculated as the average scores in the run-in period and post-baseline scores are calculated as weekly morning, afternoon, evening, and daily averages.

17. Interim Analyses

No interim analyses are planned for this study.

18. Changes from Protocol-Stated Analyses

There are no changes from the protocol-stated analyses.

19. References

Not applicable

20. Revision History

Documentation of revision to the SAP will commence after approval of the Final version 1.0.

21. Tables

Tables that will be included in the topline delivery are shown in boldface font.

Table Number	Title	Population
14.1.1	Subject Disposition	All Randomized Subjects
14.1.2.1	Demographics	mITT Population
14.1.2.2	Demographics	PP Population

Table Number	Title	Population
14.1.3	Baseline Characteristics	miITT Population
14.1.4.1	Ocular Medical History	miITT Population
14.1.4.2	Non-Ocular Medical History	miITT Population
14.1.5.1	Ocular Concomitant Medications	miITT Population
14.1.5.2	Non-Ocular Concomitant Medications	miITT Population
Exploratory Efficacy Analyses		
14.2.1.1	Corneal Fluorescein Staining (Ora Calibra® Scale)	miITT Population
14.2.1.2	Corneal Fluorescein Staining (Ora Calibra® Scale)	miITT Population with LOCF
14.2.1.3	Corneal Fluorescein Staining (Ora Calibra® Scale)	miITT Population with MCMC
14.2.1.4	Corneal Fluorescein Staining (Ora Calibra® Scale)	PP Population
14.2.2	Corneal Fluorescein Staining (NEI Scale)	miITT Population
14.2.3.1	Ocular Discomfort	miITT Population
14.2.3.2	Ocular Discomfort	miITT Population with LOCF
14.2.3.3	Ocular Discomfort	miITT Population with MCMC
14.2.3.4	Ocular Discomfort	PP Population
14.2.4	Lissamine Green Staining (Ora Calibra® Scale)	miITT Population

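### Subjects who leave before Day 15 have no post-baseline clinic efficacy data and, unless diary entries admit them to mITT, are missing from every efficacy table, including multiple imputation

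*SAP*

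**What the plan says.** - **Efficacy population.** SAP 8.3: "The analysis of baseline and all efficacy data in the Safety and Efficacy Assessment will be performed for the mITT population". Under SAP 8.1 that set "includes all randomized subjects with one post baseline efficacy assessment", and Protocol 10.1 agrees. The protocol synopsis is broader: its mITT set "includes all randomized subjects with at least one post visit 2 study assessment". SAP Section 1 settles precedence: "The statistical analysis methods presented in this document will supersede the statistical analysis methods described in the clinical protocol".
- **Missing data.** SAP 9.2 uses observed data and, for corneal staining and ocular discomfort only, adds LOCF and "Using multiple imputation methods to account for missing data". The introduction to SAP 16 gives the purpose as checking robustness. In SAP 21, Tables 14.2.1.3 and 14.2.3.3 are assigned to the "miITT Population with MCMC", and the LOCF tables are also on mITT. The per-protocol set (SAP 8.2) is the part of mITT without significant deviations that completes the study.
- **Timing.** In the SAP 4.2 schedule, the first graded staining, clinic discomfort, OSDI and VAS after Visit 2b are at Visit 3b, Day 15 ± 1.
- **Early termination.** If a subject is discontinued before the last visit, "then all safety evaluations that were to be performed at the Visit should be performed on the day of discontinuation", or at the investigator's discretion (Protocol 8.3.1). Protocol Section 4 also asks only for safety assessments and adds: "Subjects who are terminated early from the study will not be replaced".
- **Diary.** Symptoms are recorded three times a day from Day 1 and analysed under efficacy (SAP 16.14, Table 14.2.17). The diary is not listed as an efficacy variable in SAP 3.2. Protocol 8.5 describes its collection at visits from 2b to 4b.

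**The concern.** A subject who stops in the first two weeks because the drops irritate or do not help is the kind of missing subject a missing-data sensitivity analysis is meant to cover. Here that subject may be removed before the analysis begins. Membership of the analysis set would then depend on something that happens after randomisation and may be related to treatment. If early leavers in one arm are poorer responders, that arm's mean looks better than it should, and imputation within mITT cannot show by how much.

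The protocol itself foresees early departure. This is the first use of TOP1630 in man (Protocol 1), no escape medication is allowed (8.2.2), and persistent irritation or redness is a listed reason for discontinuation (5.3). The efficacy results are also meant to help power later trials (Protocol 10.3, SAP 6), so a flattered estimate could lead to an undersized next trial.

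**Working it through.** **The plan's own figure.** The only sample-size figure is the 79% probability of detecting an adverse event with a 5% rate. With 30 per arm, 1 − 0.95^30 = 0.785, so it reproduces. It concerns safety and is unaffected. No efficacy power, outcome SD or dropout rate is stated.

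**Following one subject.** Take a subject randomised at Visit 2b who leaves on Day 5.

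1. Graded staining, clinic discomfort, OSDI and VAS after baseline: none, because the next scheduled measurement is Day 15 and early termination does not require them.
2. mITT: entered only if some other record counts as an efficacy assessment. The diary might count, if returned. The SAP does not define the qualifying assessments, and neither document mentions return of the diary at early termination.
3. If not in mITT: absent from the observed-data, LOCF and multiple-imputation tables. Absent from per-protocol in any case, since that set requires completion.

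**Illustrative size.** Inputs from the documents: 30 per arm, two-sided 0.10, and a favourable difference counted as a success for that endpoint (SAP 3.4), so the chance of success with no effect is 5%. Assumed inputs: k active subjects lost, none lost on placebo, each leaver w SD worse than the remaining active subjects, no true effect.

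- Bias = (k/30) × w SD
- SE of the difference = √(2/30) = 0.258 SD
- P(success) = 1 − Φ(1.645 − bias/SE)

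For k = 2, w = 1: bias = 0.067; 0.067/0.258 = 0.258; 1 − Φ(1.387) = 8.3%.

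| k | bias, w = 0.5 | P(success) | bias, w = 1 | P(success) |
|---|---|---|---|---|
| 2 | 0.033 | 6.5% | 0.067 | 8.3% |
| 3 | 0.050 | 7.3% | 0.100 | 10.4% |
| 4 | 0.067 | 8.3% | 0.133 | 13.0% |

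Using SE = √(1/(30−k) + 1/30) instead, the w = 1 column becomes 8.2%, 10.2% and 12.6%. A milder case, one subject at 0.5 SD, gives 5.7%.

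Precision is a lesser issue. The difference detectable with 80% power, (1.645 + 0.842) × √(2/n), moves from 0.64 SD at n = 30 per arm to 0.70 SD at n = 25.

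**Would imputing everyone from baseline be enough?**

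- Under missing at random, if baseline does not predict who leaves, the leavers receive roughly their arm's observed mean and the bias stays.
- Drawing from the placebo distribution multiplies the bias by (30 − k)/30. For w = 1 and k = 2, 3, 4 the bias becomes 0.062, 0.090 and 0.116 SD, and P(success) becomes 8.0%, 9.7% and 11.6%.

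Most of the assumed bias remains. Observed data, or an imputation that explicitly assumes worse outcomes, is needed.

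**The case against.** The strongest objection is that exclusion is not established. Diary symptoms run from Day 1 and are analysed as efficacy, and nothing in the mITT definition rules them out. If a returned diary counts, a Day 5 leaver enters mITT and can have staining and discomfort imputed. The synopsis definition would admit still more subjects. This stands: a reader might infer that every subject leaving before Visit 3b is lost from every efficacy analysis, and the documents do not support that. The synopsis does not settle it, because the SAP governs analysis methods. What remains is that admission depends on an undefined term and on a diary whose return at early termination is not specified.

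A reader might also infer that nothing in the plan would expose the problem. That goes too far. SAP 10 summarises discontinuations and reasons by arm for all randomised subjects, adverse events leading to discontinuation are listed, and the efficacy listings cover all randomised subjects. Unequal dropout would be seen. Its numerical effect on the estimate would not.

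The early-termination text sets a safety minimum. It does not forbid efficacy measurements, and it gives no reason for leaving them out, so no flawed rationale should be attributed to the sponsor.

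The illustration puts all losses in one arm and in the flattering direction, and the dose is chosen after a tolerability stage that may reduce early dropout. Parts of SAP 16.1 and 16.2 are not in the public text, so imputation detail may stand there. The table list still places these analyses on mITT.

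**Conclusion.** The point holds in limited form. Subjects who leave before Day 15 have no required post-baseline clinic efficacy data. Unless diary data qualify them for mITT, they are missing from the observed-data, LOCF, multiple-imputation and per-protocol tables. The planned robustness analyses then cannot assess what early dropout does to the efficacy estimate.

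The range of about 6.5% to 13%, against 5%, rests wholly on assumptions: no true effect, 2 to 4 losses in the active arm only, and leavers 0.5 to 1 SD worse. It should not be read as a forecast. If few subjects leave early, or losses are balanced and unrelated to outcome, the effect is negligible.

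The impact is modest because efficacy is exploratory, unpowered and unadjusted for multiplicity. The change is still worth making: it is cheap, and the results are meant to inform the powering of later trials.

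**What to change.** **Main change (Protocol Section 4 and the early-termination text in 8.3.1).** Add to the early-termination visit the pre-CAE efficacy measures already taken at Visits 3b and 4b: Ocular Discomfort, the 4-symptom questionnaire, OSDI, VAS and fluorescein staining, without a CAE exposure. Collect the diary as well. These subjects would then enter mITT with observed data.

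**SAP wording.** State in 8.1 which assessments qualify for mITT, including whether the diary does, and align the synopsis. Say how an early-termination value feeds LOCF and multiple imputation, since it is not a Day 15 or Day 29 measurement.

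**Secondary change.** Run Tables 14.2.1.3 and 14.2.3.3 on all randomised subjects; Visit 2b baseline precedes randomisation. For those without a post-baseline clinic value, use a delta-adjusted imputation that assumes outcomes worse than observed, over a prespecified range such as 0.5 to 1 SD.

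**Cost.** A short protocol change, some extra time at the early-termination visit, SAP text and an additional imputation run. Not every subject will attend that visit. Pre-CAE measures cannot supply post-CAE values or the pre-to-post-CAE change, so for those endpoints the delta-adjusted analysis is the only cover.

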9.3 Definition of Baseline

Baseline measures are defined as the last measure prior to the initiation of study treatment, usually at Visit 2b. If a measure is taken both pre-CAE® and post-CAE®, the baseline will be the time point matched value at Visit 2b. For measures from daily subject diaries, baseline is defined as the average of all available days' readings during the run-in period, where daily scores are first obtained by averaging the AM and PM scores for that day, as applicable. For changes from pre-CAE® to post-CAE® post first treatment, the change from pre-CAE® to post-CAE® at Visit 2b will be considered the baseline value. For purposes of analysis, only subjects with at least 5 days of data in the run-in period will be included in change from baseline summaries and analyses.

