#### **Post- CAE® Procedures**

- Ora Calibra® Ocular Discomfort
- Ora Calibra® Ocular Discomfort & 4-Symptom Questionnaire
- Slit-lamp biomicroscopy
- Ora Calibra® Conjunctival Redness
- TFBUT
- Fluorescein staining – Ora Calibra® and NEI scale
- Lissamine Green staining – Ora Calibra® and NEI scale
- Intraocular pressure (non-contact)
- Undilated fundoscopy
- Review of qualification criteria
- Adverse event query
- Dispensation of run-in (RUN-IN) for TID dosing until Visit 2b;
  - Subjects will be instructed to dose in each eye three times daily (morning, afternoon, and in the evening before bed);
- Dispensation of diaries and subject instructions;

- Subjects will be instructed to complete their diary and dose in each eye in the afternoon and before bed on the evening of Visit 1b
- Subjects will be instructed to complete diary symptoms TID prior to drop instillation in the morning, afternoon, and evening before bed until Visit 2b
- Subjects will be instructed to complete their diary on the morning of their next visit (Visit 2b)
- Subjects will be instructed to not dose with run-in placebo on the morning of their next visit (Visit 2b)
- Qualified subjects will be scheduled for Visit 2b.

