### **Subject Diary**

Subjects will be instructed to complete diary TID prior to each dose. Subjects will also indicate if their dose was taken.

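### SAP 9.3 builds one diary baseline from AM and PM scores, while SAP 16.14 analyses morning, afternoon, evening and daily averages, so within-arm diary change is not like-for-like unless symptoms are flat over the day.

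*SAP*

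**What the plan says.** **Collection.** The diary is filled in three times a day, run-in included. SAP 16.14 says "subjects will grade the severity of their dry eye symptoms in their diary in the morning, afternoon and evening prior to each dose". For the run-in, the protocol's Visit 1b post-CAE procedures (section 8.3.1) say "Subjects will be instructed to complete diary symptoms TID prior to drop instillation in the morning, afternoon, and evening before bed until Visit 2b". Protocol Appendix 2, Subject Diary, agrees: "Subjects will be instructed to complete diary TID prior to each dose".

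**Baseline.** SAP 9.3 has the only explicit derivation. For diary measures it takes a single mean over whatever run-in days a subject has, "where daily scores are first obtained by averaging the AM and PM scores for that day"; a closing qualifier limits this to where it is applicable. The preceding sentence of 9.3 sets a different rule for measures taken before and after CAE exposure: "the baseline will be the time point matched value at Visit 2b".

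**Follow-up.** SAP 16.14 analyses the morning, afternoon, evening and daily average scores separately: "post-baseline scores are calculated as weekly morning, afternoon, evening, and daily averages". There, in SAP 16 and in protocol 10.4.7, the baseline is described only as the run-in average, with no time of day. No section defines a morning, afternoon or evening baseline, or lists the readings that enter the daily average.

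**Use.** SAP 9.4 defines change as follow-up minus baseline. SAP 9.3 admits to change-from-baseline summaries only subjects with at least 5 days of run-in data.

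**The concern.** A two-reading baseline rule has been attached to a three-reading diary with four follow-up scores. If a programmer applies SAP 9.3 as written, the evening weekly average is set against a mean that also contains the morning. The afternoon average is set against a mean that, on the plain reading of AM and PM, contains no afternoon score.

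Any regular daily pattern in symptoms would then appear in the tables as improvement at one time of day and worsening at another, in both arms. Two programmers could also derive different diary baselines from the same text. The trial is meant partly to supply efficacy data for sizing later studies, so the reported changes and their spread may be used again.

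**Working it through.** **No plan figure to reproduce.** The documents give no diary effect size, SD or power. The one sizing figure, 79% for adverse events, follows from 30 per arm (1 - 0.95^30 = 0.785) and has no bearing on this point.

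**Step 1: offset with no true change.** Let M, A and E be a subject's mean morning, afternoon and evening scores, the same in run-in and follow-up. The symptom scale is redacted, so the profiles below are assumptions. Reading PM as evening, the SAP 9.3 baseline is B = (M + E)/2. The apparent changes are M - B, A - B, E - B and, if the daily score uses all three readings, (M + A + E)/3 - B.

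| M / A / E | B | Morning | Afternoon | Evening | Daily (3 readings) |
|---|---|---|---|---|---|
| 2 / 2 / 2 | 2.0 | 0 | 0 | 0 | 0 |
| 2.0 / 2.5 / 3.0 | 2.5 | -0.5 | 0 | +0.5 | 0 |
| 2 / 2 / 3 | 2.5 | -0.5 | -0.5 | +0.5 | -0.17 |
| 2 / 3 / 3 | 2.5 | -0.5 | +0.5 | +0.5 | +0.17 |

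If PM means the average of afternoon and evening, then B = (M + (A + E)/2)/2. For 2.0/2.5/3.0 this is 2.375, and the changes are -0.375, +0.125, +0.625 and +0.125. The mismatch stays. With a baseline matched by time of day, every entry is 0.

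**Step 2: between-arm comparison.** The offset does not depend on treatment, so it cancels in the difference between arms. A simulation checked this for the morning score, with 30 per arm, 4,000 trials and a 2.0/2.5/3.0 profile. The assumed SDs were 0.8 for subject, 0.4 for subject shift at follow-up, and 0.34 (run-in) and 0.3 (follow-up) for reading noise. With no true effect, the mean difference was within 0.003 of 0 for both baselines.

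**Step 3: precision.** In the same simulation, the SE of the ANCOVA difference was:

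| Between-subject SD of time-of-day pattern | AM/PM baseline | Matched baseline |
|---|---|---|
| 0 | 0.147 | 0.158 |
| 0.3 | 0.155 | 0.155 |
| 0.6 | 0.182 | 0.155 |

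A closed form covers the afternoon as well. Assume subject variance 1, subject-by-time-of-day variance s, subject-by-period variance p, day-to-day variance e (0.5 or 1) and 7 diary days. The residual variance is Var(Y) - Cov²/Var(B).
- Matched baseline: Var(Y) = Var(B) = 1 + s + p + e/7, Cov = 1 + s.
- AM/PM baseline: Var(B) = 1 + s/2 + p + e/14, with Cov = 1 for afternoon and 1 + s/2 for morning or evening.

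Example, afternoon, s = 0.25, e = 0.5, p = 0: Var(Y) = 1.3214. The matched residual is 1.3214 - 1.25²/1.3214 = 0.139. The AM/PM residual is 1.3214 - 1/1.1607 = 0.460. The ratio is 3.3. With p = 0.3 the residuals are 0.658 and 0.937, a ratio of 1.4.

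| Residual variance, AM/PM over matched | p = 0 | p = 0.3 | p = 0.5 |
|---|---|---|---|
| Afternoon, s = 0.10 to 0.25 | 1.30 to 3.31 | 1.11 to 1.42 | 1.07 to 1.27 |
| Morning or evening, s = 0.10 to 0.25 | 0.96 to 1.66 | 1.01 to 1.15 | 1.01 to 1.10 |
| Any time of day, s = 0 | 0.77 to 0.78 | 0.95 to 0.97 | 0.97 to 0.98 |

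The ratio falls on either side of 1, depending on variances that the documents do not give.

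**The case against.** **The rule may be loose wording, not a design choice.** SAP 9.3 says as applicable, and PM could cover both later readings. SAP 16.14 names the four scores and then refers to run-in averages, which can be read as the run-in average of the same score. Part of 16.14 is also missing from the available text. All of this is fair. But 16.14 does not state that reading, 9.3 has the only explicit derivation, and neither meaning of PM yields a baseline by time of day. The two sections would still need reconciling.

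**A pooled run-in mean is a legitimate covariate.** This stands. Time-point matching in 9.3 is written for pre- and post-CAE measures only, so the diary rule breaks no general principle of the SAP. In ANCOVA a constant offset goes into the intercept. The t-test on individual symptoms in 16.14 names no baseline.

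**Stronger readings that the documents do not support.** A reader might infer that the daily average sets three readings against two. No section says which readings form the follow-up daily score; if the 9.3 rule is used in both periods, that score is like-for-like. A reader might also infer that every diary change is distorted, but the offset is 0 for a flat day and can be 0 for single scores. Finally, a reader might infer a large loss of precision. The ratio of 3.3 arises only if a subject's true level is identical in run-in and follow-up.

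**The stakes are limited.** The study is not powered for efficacy, the key endpoints for imputation are corneal staining and ocular discomfort, and the diary is not in the SAP 3.2 variable list. That also stands.

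**Conclusion.** The point holds as a mismatch between a stated rule and the data it governs. Under SAP 9.3 as written, within-arm change for a morning, afternoon or evening diary score includes the gap between that time of day and the AM/PM mean. The gap was up to 0.5 points in the assumed profiles with PM read as evening, and 0.625 in the one shown with PM read as afternoon and evening together. It is 0 if symptoms do not vary over the day, and the true size cannot be known from the documents.

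The randomised comparison is not biased in expectation. No general precision loss can be claimed for the time-of-day scores, because its direction depends on assumed variances. What suffers is the interpretation of within-arm change and the reproducibility of the derivation, for an exploratory endpoint without a power claim. The correction is still worth making because it costs little and must precede unmasking.

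**What to change.** Before unmasking, amend SAP 9.3 and 16.14 together:

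1. Define the baseline for each diary score (morning, afternoon, evening, daily) as the run-in average of that same score. Use it both for change from baseline and as the ANCOVA covariate.
2. State that the daily score averages all available morning, afternoon and evening readings, in run-in and follow-up alike.
3. Add a rule for partial days. Under the protocol's Visit 1b instructions, that day has afternoon and evening entries only, and the Visit 2b day has only a morning run-in entry. The rule should say whether such days enter the daily average and count towards the 5-day minimum.

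The cost is SAP wording and minor programming on data already collected. The downside is that a baseline for one time of day uses fewer readings than an all-day mean. When subjects share one daily pattern it can be slightly noisier, as in the simulated SE of 0.158 against 0.147.
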